### **Analysis of the Secondary Endpoints**

The following safety and clinical outcomes will be evaluated.

The safety and clinical outcomes assessments include:

1. Hernia recurrence up to 12 months following surgery.
2. Hernia mesh fixation at time of surgery.
3. Approximation of the peritoneum at time of surgery (TAPP repairs only).
4. Quality of Life following groin hernia repair as measured by Carolinas Comfort Scale at baseline and at 7 days, 14 days, 1 month, 3 months, 6 months, 9 months and 12 months following laparoscopic (TEP and TAPP) groin hernia repair.
5. Subject pain following groin hernia repair as reported by VAS at screening, discharge and at 7 days, 14 days, 1 month, 3 months, 6 months, 9 months and 12 months following surgery.
6. Rate of device and procedure-related adverse events reported throughout the duration of the study.

To test the secondary endpoints #1, 2, and 3, a binomial non-inferiority test will be run using SAS Proc Freq with the Farrington-Manning method on the PP set. A p-value of  $< 0.025$  from the binomial non-inferiority test will be considered evidence that LiquiBand FIX8® is not inferior to AbsorbaTack™. Confidence interval on the difference of the rates will be reported and non-inferiority is indicated if the upper limit of the confidence interval is less than the non-inferiority margin. ITT analyses will be performed for the three secondary endpoints with hypothesis statements as supporting sensitivity analyses.

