| Objectives:             | 
Primary:
 

1. To compare the improvement in pain following groin hernia repair by LiquiBand FIX8® to control device as measured by Visual Analog Scale (VAS) at baseline (worst pain experienced within 1 month of screening visit) and at six months post hernia repair.

 
Secondary:
 

1. To evaluate the incidence of hernia recurrence in patients following laparoscopic (TEP and TAPP) hernia repair using LiquiBand FIX8® or control device at 6 months post hernia repair.

2. To compare the use of LiquiBand FIX8® to control device for mesh fixation at time of surgery.

3. To compare the use of LiquiBand FIX8® to control devices for the approximation of the peritoneum (TAPP repairs only) at time of surgery.

4. To evaluate the quality of life experienced by subjects following groin hernia repair by LiquiBand FIX8® or control as measured by the Carolinas Comfort Scale (CCS) at baseline (prior to surgery), and at 1 week, 2 weeks, 1 month, 3 months, 6 months, 9 months and 12 months following surgery.

 |

5. To compare levels of pain experienced following laparoscopic (TEP and TAPP) groin hernia repair by LiquiBand FIX8® or control device, as measured by VAS at discharge, and at 1 week, 2 weeks, 1 month, 3 months, 6 months, 9 months and 12 months following surgery.
6. To evaluate the safety of LiquiBand FIX8® and control device for groin hernia repair by comparing incidence of all adverse events in patients post laparoscopic groin hernia repair.

**Number of patients:** 284 (142 per treatment arm)

**Investigational centers:** Up to 10 investigational centers will be recruited for this study, including the following institutions:

1. University of Kentucky
2. The Ohio State UniversityPrisma Health – Upstate
3. Overlake Medical CenterCleveland Clinic
4. Prisma Health – Upstate
5. Overlake Medical Center
6. Cleveland Clinic

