## ENDPOINTS

**Table 1:** Primary and Secondary Efficacy and Safety Endpoints of the Investigational Study

| Table 1: Primary and Secondary Efficacy and Safety Endpoints of the Investigational Study |   |
|--|---|
| Primary Efficacy 1   | Effectiveness of LiquiBand FIX8® will be assessed and compared to treatment with AbsorbaTack™ in subjects requiring laparoscopic (TEP and TAPP) hernia repair. Success will be determined by improvement in pain not inferior to control device as measured by a VAS value (0 = no pain to 10 = most pain imaginable) from baseline (worst pain experienced within 1 month of screening visit) to six months post hernia repair.  |
| Secondary Efficacy 1   | The incidence of hernia recurrence in patients following laparoscopic (TEP and TAPP) groin hernia repair by LiquiBand FIX8® or control (AbsorbaTack™) will be assessed by physical examination at 2 weeks, 3 months, and 6 months and evaluated following the 6 month timepoint. Suspected hernia recurrence will also be evaluated at any time following surgery and up to the 12 month follow up visit if reported by the subject. Suspected hernia recurrence will be confirmed by ultrasound imaging following physical examination.  |
| Secondary Efficacy 2   | LiquiBand FIX8® will be required to successfully fix hernia mesh in patients undergoing TEP and TAPP laparoscopic groin hernia repair, at a rate non-inferior to control device (AbsorbaTack™) in order to meet this end point. Successful mesh fixation would not require any additional fixation by alternate fixation device. Unsuccessful mesh fixation is defined as requiring the use of an alternative fixation device or additional procedure to achieve adequate fixation.   |
| Secondary Efficacy 3   | LiquiBand FIX8® will be required to successfully approximate the peritoneum in patients undergoing laparoscopic TAPP hernia repair, at a rate non-inferior to control devices in order to meet this end point. Successful peritoneal closure would not require any additional fixation by alternate fixation device or additional procedure. Unsuccessful peritoneal closure is defined as requiring the use of an alternative fixation device or additional procedure to achieve adequate fixation. Investigators in the study will be able to use AbsorbaTack™, sutures or staples for closure of the peritoneum. |

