| Secondary Efficacy 4   | Quality of Life will be assessed by completion of the Carolinas Comfort Scale (CCS) Questionnaire prior to surgery and at 1 week, 2 weeks, 1 month, 3 months, 6 months, 9 months and 12 months following laparoscopic (TEP and TAPP) groin hernia repair. CCS scores at each timepoint will be compared between the LiquiBand FIX8® and control (AbsorbaTack) treatment groups.   |
| Secondary Efficacy 5   | Evaluation of pain will be measured by VAS (0 = no pain to 10 = most pain imaginable) at baseline (pre-surgery), at discharge, and at 1 week, 2 weeks, 1 month, 3 months, 6 months, 9 months and 12 months post surgery.  |
| Secondary Safety 1   | The incidence of all adverse events whether or not determined to be related to the LiquiBand FIX8® device or control device (AbsorbaTack™) will be assessed intraoperatively, at discharge, and at each follow-up visit throughout the study, or for cause at any time in the follow up period.   |

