## Statistical Analysis

### General Approach

The primary efficacy endpoint will be tested for non-inferiority of treatment to control with a predefined non-inferiority margin of 0.9 on the VAS scale. Confounding factors for the pain score including analgesic use or other pain management therapies will be measured at screening and all follow up visits, and compared between treatment arms to ensure proper balance within each site. The study will be claimed successful if both PP and ITT analyses on the primary efficacy endpoint showed significance at 0.025. Once the hypothesis tests succeed for both analysis sets on the primary efficacy endpoint, key secondary endpoints will be compared between treatments sequentially in a non-inferiority manner. The following sequential analysis approach will be taken:

- Primary non-inferiority on the PP set; if significant at one-sided alpha=0.025, and
- Primary non-inferiority on the ITT set; if significant at one-sided alpha=0.025, then proceed to key secondary endpoints detailed in Section 3.1.
- Secondary non-inferiority on the PP set on Hernia Recurrence rate in subjects following laparoscopic (TEP and TAPP) groin hernia repair by LiquiBand FIX8® or control (AbsorbaTack™) at 6 months, at one-sided alpha=0.025.
- Secondary non-inferiority on the PP set on Rate of successful hernia mesh fixation in subjects undergoing TEP and TAPP laparoscopic groin hernia repair; if significant at one-sided alpha=0.025, then
- Secondary non-inferiority on the PP set on Rate of successful peritoneal closure in subjects undergoing laparoscopic TAPP hernia repair; if significant at one-sided alpha=0.025, then

The family-wise type I error will therefore be controlled at 0.025.

Summary statistics will consist of the number and percentage of responses in each category for discrete variables, and the mean, median, standard deviation (SD), minimum, and maximum for continuous variables. One-sided statistical tests will use a significance level of  $\alpha = 0.025$ , and two-sided tests will use a significance level of  $\alpha = 0.05$ .

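### The safety analysis covers only device- and procedure-related adverse events, but the safety endpoint is all adverse events

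*Combined protocol and SAP*

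**What the plan says.** The safety endpoint is described in three places in the combined protocol and SAP.

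- Clinical Investigation Summary, Objectives, secondary objective 6: safety of the two devices is evaluated "by comparing incidence of all adverse events in patients post laparoscopic groin hernia repair".
- Endpoints, Table 1 (titled "Primary and Secondary Efficacy and Safety Endpoints of the Investigational Study"), Secondary Safety 1: "The incidence of all adverse events whether or not determined to be related to the LiquiBand FIX8® device or control device (AbsorbaTack™"), assessed during surgery, at discharge and at each follow-up visit. This is the only safety endpoint in the table.
- Analysis of the Secondary Endpoints, item 6: "Rate of device and procedure-related adverse events reported throughout the duration of the study".

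The list that contains item 6 opens with "The safety and clinical outcomes assessments include". That section names a test for items 1 to 3 only. Under Statistical Hypotheses, the list of secondary endpoints has no adverse-event bullet. General Approach gives a summary format ("Summary statistics will consist of the number and percentage of responses in each category for discrete variables") but does not say which adverse events are to be summarised.

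**The concern.** Table 1 sets relatedness aside as a condition of the endpoint, and the analysis item brings it back. Someone programming the tables from the analysis section would produce a related-event rate and could take it to be the analysis of Secondary Safety 1, which it is not.

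Two things are at stake.

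- Demonstrating safety is part of the trial's stated purpose. A related-only rate says nothing about a difference between arms in events judged unrelated.
- The all-event incidence does not depend on anyone's view of causality, but the related-event rate does. The study is single blinded, and the Schedule of Study Assessments (footnote 5) requires blinding of the patient only.

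With two definitions on file, the choice of which to report as the safety result could also be made after the data are seen.

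**Working it through.** The plan states no figure to reproduce. The check compares texts, with simple counts.

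**Step 1. Does item 6 stand for Secondary Safety 1?** Table 1 has 1 primary efficacy + 5 secondary efficacy + 1 secondary safety = 7 endpoints, of which 6 are secondary. The analysis list also has 6 items:

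| Item | Secondary endpoint in Table 1 | Item in Analysis of the Secondary Endpoints | Narrower than the endpoint? |
|---|---|---|---|
| 1 | Efficacy 1: recurrence, evaluated after month 6, suspected cases followed to month 12 | Recurrence to month 12 | No |
| 2 | Efficacy 2: mesh fixation | Mesh fixation at surgery | No |
| 3 | Efficacy 3: peritoneal closure, TAPP | Peritoneal closure at surgery, TAPP | No |
| 4 | Efficacy 4: Carolinas Comfort Scale, before surgery and 7 follow-up times | Same scale, same times | No |
| 5 | Efficacy 5: VAS pain before surgery, at discharge and at 7 follow-up times | Same measure, same times | No |
| 6 | Safety 1: all adverse events | Device- and procedure-related adverse events | **Yes** |

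Row 5 shows the pattern: "Evaluation of pain will be measured by VAS" in Table 1 becomes "Subject pain following groin hernia repair as reported by VAS at screening, discharge" and the later visits in the analysis list, with nothing dropped. The order matches throughout. Item 6 is the only one of 6 that is narrower than its endpoint, and 0 of 6 items name all adverse events.

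**Step 2. Could the two wordings mean the same set?** Naming procedure-related events makes item 6 wider than device-related events alone. It still leaves out events judged unrelated to either, which Secondary Safety 1 expressly includes. The item 6 set is therefore a subset of the endpoint set.

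**Step 3. What is left out?** Within an arm, each subject with at least one adverse event either has at least one related event or has only unrelated events. So, as proportions of subjects,

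p(any event) = p(at least one related event) + p(unrelated events only),

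and the difference between arms splits the same way:

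Δ(any) = Δ(related) + Δ(unrelated only).

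The endpoint calls for Δ(any). Expressed in subjects, item 6 gives Δ(related). The last term is not reported, and the documents contain nothing from which to put a number on it.

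**Step 4. Does other text fill the gap?** Statistical Hypotheses has no adverse-event bullet. The testing sequence in General Approach does not cover adverse events. The summary-statistics sentence sets a format and not a scope. Item 6 is the only adverse-event analysis in the statistical sections.

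**Step 5. Are the data there?** The Schedule of Study Assessments has adverse-event evaluation at visits 2 to 10, which is 10 − 2 + 1 = 9 scheduled visits, with no limit by relatedness. The gap is in the planned analysis and not in data capture.

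**The case against.** The best reply is that the all-event comparison is already promised. Protocol and SAP are one document, objective 6 and Table 1 commit to all adverse events, and item 6 does not revoke them. The list is introduced as a non-exhaustive one, and General Approach supplies a format for an all-event table. These lists are also loose elsewhere: item 1 runs to 12 months while the recurrence hypothesis is at 6 months, and the Statistical Hypotheses list omits VAS pain as well as adverse events. On this view the mismatch is loose wording and not a decision to narrow the endpoint.

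Much of this is fair. An all-event table is not excluded, and nothing shows that the narrowing was intended. But a table that is merely permitted is not a planned analysis. The one adverse-event item in the analysis text still conflicts with the endpoint in whose place it stands. The looseness of item 1 makes it wider than its endpoint, not narrower.

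Two further points stand as limits. The documents do not say who judges relatedness, so dependence on an unblinded judgement is a risk and not an established bias. And part of the plan may not be visible: General Approach refers to a Section 3.1 that does not appear under that number. The contradiction, however, is between texts that are all present, so it does not rest on anything missing.

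**Conclusion.** The concern holds. Item 6, as worded, does not estimate the trial's only safety endpoint. It estimates a subset defined by a relatedness judgement that the endpoint sets aside.

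The effect is confined to safety reporting. Adverse events carry no hypothesis test and lie outside the testing sequence, so the primary result, the sample size of 284 and the one-sided 0.025 error control are unaffected. How much would go unreported is unknown. The conclusion rests on reading item 6 as the analysis of Secondary Safety 1, which the section heading and the one-to-one order of the six items support. It should be corrected before the analysis, but it does not threaten the trial's main conclusion.

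**What to change.** Reword item 6 in Analysis of the Secondary Endpoints as the incidence of all adverse events by arm, regardless of relatedness. Report the number and percentage of subjects with at least one event, in the format that General Approach already gives for discrete variables. Keep device- and procedure-related events as a stated subset of that table. A descriptive difference between arms with a 95% confidence interval is optional.

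Two small additions would complete the change: name the analysis set for adverse events, since the section assigns sets only to items 1 to 3, and add an adverse-event bullet to the secondary list under Statistical Hypotheses.

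The core change costs one line of SAP text and one table from data already scheduled at visits 2 to 10. The sample size and the sequential tests stay as they are.

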### Population for Analysis

The following subject populations will be created:

- Intent-to-Treat (ITT): All enrolled subjects. ITT analysis will be per randomized group irrespective of the treatment actually received.
- Per Protocol (PP): All ITT subjects excluding those with major protocol violations. PP analysis will be per actual treatment group which is the same as the treatment initially randomized.
- As the PP analysis is more conservative for non-inferiority hypothesis, all hypotheses will be tested with the PP population. ITT analysis will also be performed for all hypotheses, as the primary analysis for the primary endpoint, and the supportive analysis for secondary endpoints with non-inferiority hypothesis.

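### Mesh fixation and peritoneal closure are decided on PP alone as the conservative set, but the failure event bears on PP membership and nothing secures that failures stay in

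*Combined protocol and SAP*

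**What the plan says.** Three sections make PP the deciding set for the secondary hypotheses. Population for Analysis gives the reason: "As the PP analysis is more conservative for non-inferiority hypothesis, all hypotheses will be tested with the PP population". General Approach sets the steps of the sequence, for example "Secondary non-inferiority on the PP set on Rate of successful hernia mesh fixation", with the same wording for peritoneal closure. Analysis of the Secondary Endpoints places the Farrington-Manning test on PP and adds that "ITT analyses will be performed for the three secondary endpoints with hypothesis statements as supporting sensitivity analyses". For the primary endpoint, by contrast, General Approach requires significance on both PP and ITT.

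The sets are defined in Population for Analysis. On ITT: "ITT analysis will be per randomized group irrespective of the treatment actually received". On PP: "Per Protocol (PP): All ITT subjects excluding those with major protocol violations", and "PP analysis will be per actual treatment group which is the same as the treatment initially randomized". The visible text does not say what makes a violation major.

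Table 1 under Endpoints defines the two failure events. Secondary Efficacy 2: "Unsuccessful mesh fixation is defined as requiring the use of an alternative fixation device or additional procedure to achieve adequate fixation". Secondary Efficacy 3: "Unsuccessful peritoneal closure is defined as requiring the use of an alternative fixation device or additional procedure to achieve adequate fixation". The closure entry also lets investigators close the peritoneum with AbsorbaTack, sutures or staples, without saying in which arm.

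**The concern.** PP is usually preferred for non-inferiority because non-adherence tends to make the arms look alike, and removing it restores contrast. That reasoning presumes that leaving PP is not driven by the outcome under test. For these two endpoints it may be, because the failure event is itself a departure from sole use of the assigned device.

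Two kinds of failure need separating. A subject given the assigned device plus extra fixation did receive the randomized treatment, so the PP rule does not clearly remove that subject. A subject switched entirely to another device can be read as someone whose actual treatment is not the randomized one, and so as outside PP. ITT keeps both.

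If switched subjects were left out, PP would understate the failure rate. The ITT run would show this but could not stop the claim. For closure the position is less clear still. Because several closure methods are permitted, it is uncertain what counts as a departure in the control arm, and exclusions could fall unevenly between arms. At stake are the two device-performance claims.

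**Working it through.** **Inputs from the documents.** 142 subjects per arm (Number of patients). 148 TAPP subjects (Analysis of the Primary Efficacy Endpoint). Margins of 10 points for fixation and 15 points for closure (Statistical Hypotheses). One-sided 0.025 and the Farrington-Manning method.

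**Assumptions.** An equal split of the TAPP cohort, 148/2 = 74 per arm. A control failure rate of 5%, varied from 2 to 10%. A share f of failures left out of PP. The documents give no expected success rate, power or exclusion share for these endpoints, so there is no plan figure to reproduce.

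**Test.** On failure rates, z = (p_T − p_C − M)/SE, where M is the margin and SE uses the two rates estimated under the restriction p_T − p_C = M. The one-sided p is Φ(z), and non-inferiority is met if p < 0.025.

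**Step 1: hypothetical counts near the threshold (no true rate assumed).**

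| Endpoint and set | Test vs control failures | z | p | Met? |
|---|---|---|---|---|
| Fixation, all kept | 13/142 vs 7/142 | (0.0915 − 0.0493 − 0.10)/0.0328 = −1.76 | 0.039 | No |
| Fixation, one test-arm failure out | 12/141 vs 7/142 | (0.0851 − 0.0493 − 0.10)/0.0327 = −1.97 | 0.0246 | Yes |
| Closure, all kept | 9/74 vs 4/74 | (0.1216 − 0.0541 − 0.15)/0.0506 = −1.63 | 0.052 | No |
| Closure, one out | 8/73 vs 4/74 | (0.1096 − 0.0541 − 0.15)/0.0505 = −1.87 | 0.031 | No |
| Closure, two out | 7/72 vs 4/74 | (0.0972 − 0.0541 − 0.15)/0.0505 = −2.12 | 0.017 | Yes |

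One excluded failure can reverse the fixation decision. The closure example needs two.

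**Step 2: stand-alone one-sided error.** Control failure is 5% and test-arm failure is 5% + M, so 15% for fixation and 20% for closure. Each failure leaves PP with probability f in both arms. The error is the exact sum of binomial probabilities over outcomes that pass.

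| f | Fixation, PP alone | Fixation, both sets | Closure, PP alone | Closure, both sets |
|---|---|---|---|---|
| 0 | 2.3% | 2.3% | 2.4% | 2.4% |
| 5% | 3.0% | 2.1% | 2.9% | 2.2% |
| 10% | 3.9% | 2.1% | 3.6% | 2.1% |
| 25% | 8.4% | 2.1% | 7.4% | 2.1% |

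With control failure of 2 to 10%, the 25% row for PP alone spans 6.7 to 9.9% (fixation) and 6.3 to 8.2% (closure). Requiring both sets stays within 1.9 to 2.6%.

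**Step 3: uneven exclusion.** If exactly two test-arm failures and no control failures are left out, at 5% control failure, PP-alone error is 5.5% (fixation) and 6.4% (closure).

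These errors are for each test taken alone. Having to pass the primary and the earlier secondary steps first lowers the chance of reaching them.

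**The case against.** The strongest reply is that the harm depends on a reading the plan never states. Table 1 prospectively counts use of another device or an additional procedure as the failure outcome, and an outcome the protocol anticipates is not naturally a violation of it. This stands, and the natural reading keeps these subjects in PP as failures. A reader might infer that PP strips out every failure. The documents do not support that: it would leave 100% success in both arms, which cannot be intended, and supplemented subjects did receive the assigned device.

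The permitted closure methods also make it less likely that their use would be called a major violation. That too is fair, but the same sentence leaves a control-arm departure undefined, so it does not settle PP membership.

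A fuller definition of violations may exist elsewhere, since General Approach cites a Section 3.1 that the visible text does not contain. The absence of a definition is therefore not the criticism. The criticism is that the decision rule relies on PP being conservative for an event that can itself affect PP membership.

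The counts above were chosen near the threshold, and the effect is modest at small exclusion shares. With 5% true failure in both arms and 10% of failures excluded, PP passed while ITT failed in about 2.0% (fixation) and 1.1% (closure) of simulated trials. This also stands, and it limits the size of the point.

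Finally, ITT will be reported, so a discrepancy would be seen. But being seen is not the same as being able to block the claim.

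**Conclusion.** The point holds as an unsecured decision rule, not as a demonstrated bias. For fixation and closure, the plan's ground for letting PP decide alone is not assured, because a literal reading of the PP rule can drop fully switched failures and the ITT analysis has no veto. If all failures stay in PP, error remains near 2.3 to 2.4% and nothing is lost. If 5 to 25% were left out, it would rise to about 3.0 to 8.4% (fixation) and 2.9 to 7.4% (closure), given 5% control failure, a true deficit on the margin and equal exclusion in both arms. The last assumption is doubtful for closure.

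A reader might also infer that trial success is at risk, or that recurrence shares the problem. Neither follows. Success rests on the primary endpoint, where both sets must pass, and recurrence is not defined by a change of device. The point should be fixed, but it is confined to two secondary claims.

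**What to change.** In Population for Analysis, General Approach and Analysis of the Secondary Endpoints, require non-inferiority on both ITT and PP for mesh fixation and peritoneal closure, as General Approach already does for the primary endpoint. Add one sentence: use of an alternative fixation device or additional procedure that meets the Table 1 failure definition counts as an endpoint failure and is not a ground for PP exclusion in these two analyses. The sentence alone closes this route. The both-sets rule also covers other PP exclusions whose definition is not visible. Recurrence stays as planned.

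The change is to wording only, since the ITT runs are already planned, and should be made before unblinded analysis. The cost is a little power. In 400,000 simulated trials with 5% or 10% of subjects left out of PP at random (assumed), moving from PP alone to both sets gave, at 95% true success in both arms:

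- fixation: 93.0% to 92.3%, and 91.5% to 90.7%;
- closure: 94.1% to 93.6%, and 92.7% to 92.1%.

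At 90% success the loss is 1.3 to 2.1 points. At 98% it is under 0.1 point.
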